3.2 Secondary outcomes

The secondary outcomes are described in detail in Table 1 below.

4. Background

Black individuals in the United States fare worse than White individuals across almost every social, economic, and health indicator. The Black health disadvantage starts at birth, reflecting the cumulative toll of racialized social stressors and healthcare discrimination on maternal health and resulting in higher rates of preterm birth and low birth weight. Black youth are disproportionately exposed to environmental toxins such as lead and adverse childhood events such as financial hardship and neighborhood violence. Black adults have higher rates of chronic disease, including diabetes, hypertension, as well as many cancers. These and other forces culminate in a stark racial longevity gap: in Philadelphia, the location of this study, life expectancy for people living in a poor, predominantly Black neighborhood is 20 years lower than for people living in a nearby affluent, predominantly White neighborhood.

The fundamental cause of these striking and pervasive disparities is structural racism – the confluence of deep historical, institutional, cultural, and ideological forces that unequally distribute resources and risks across racialized groups⁻ Structural racism patterns health by affecting a range of interconnected, mutually reinforcing social determinants of health at the national, neighborhood, household, and individual levels. Most notably, longstanding, systematic disinvestment has resulted in highly segregated Black neighborhoods with dilapidated

environmental conditions and severe economic insecurity within Black households, leading to a "feedback loop of concentrated racial disadvantage," all of which have been strongly tied to poor health.

Most interventions seeking to address racial health disparities focus on individual-level behaviors and outcomes, or individual channels by which structural racism harms health. However, by failing to address upstream social determinants, these interventions have had limited population level impact. A multi-level, multi-component intervention package focused on a range of social determinants of health is necessary to meaningfully address structural racism as a fundamental cause of racial health disparities.

5. Study design

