Our two primary outcomes will focus on (1) overall health and (2) psychological distress. Our measure of overall health comes from an index based on responses to three survey questions: a self-reported rating of the participant's general health (on a 5 point Likert scale, ranging from poor to excellent); the self-reported number of days in the last 30 in which poor physical or mental health precluded engagement in the participant's usual activities; and a self-reported rating change in overall health outcomes over the last 12 months (three point scale denoting worse, same, or better). We will use the method of Anderson (2008) to create a single (standardized) index of overall health.⁷ This method uses the inverse covariance matrix of the variables to create the index and allows for missing observations.

Our measure of psychological distress is the Kessler-6 scale, a validated measure of non-specific psychological distress represented by the summed score of six questions querying the frequency of symptoms of feeling nervous, hopeless, depressed, restless, depressed, that everything was an effort, and worthless over the past 30 days.⁸ The Kessler-6 ranges from 0-24.

Secondary child health outcomes

In addition to the outcomes listed above, we plan to evaluate a series of secondary outcomes focused on child health and well-being, derived from a follow-up survey administered to participants with children ages 3 to 17 at the time of 24-month follow-up. These will include caregiver-reported child health, health care utilization, and several outcomes related to child well-being, neighborhood safety for children, and parenting, as listed in Table 2.

We will also examine additional child health outcomes for all children residing in IGNITE study clusters using secondary analysis of existing data sets. Specifically, we will assess school attendance and performance for all cluster residents using Philadelphia school district data, birth outcomes for cluster residents using Pennsylvania birth certificate data, and health care utilization outcomes for all cluster residents using electronic health record data from the Children's Hospital of Philadelphia. These outcomes are also included in Table 2. We will obtain separate approval from the Children's Hospital of Philadelphia Institutional Review Board prior to abstraction of electronic health record data for these child health outcomes.

Power Calculations

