For secondary outcomes based on microcluster-level administrative data, we will use a difference-in-differences strategy, which leverages additional power from repeat (quarterly) observations that are available in administrative data.¹⁶ Specifically, we will estimate a Poisson-fixed effects model for each secondary outcome on the interaction between binary indicators for calendar time (quarter-year) and binary indicator of intervention status, adjusting for cluster and calendar time (quarter-year) fixed effects (the cluster fixed effect subsumes the main effect for treatment status); microcluster populations at baseline will be used as the exposure terms. This approach is known as an event study specification.¹⁷ The time period of analysis will comprise the 8 quarters prior to intervention and all quarters over the course of the intervention period, which comprises the duration between the end of enrollment and baseline survey data collection to the beginning of follow-up data collection, and the post-intervention period, which all quarters between the beginning and end of follow-up survey data collection. (As data becomes available, we will, in the future, also conduct separate analysis that includes periods 8 quarters after the end of survey data collection, once these data become available. This analysis will be viewed as an extension of our primary difference-in-differences model to assess whether treatment effects were sustained after intervention period ended.)

The coefficients on the terms interacting treatment status with time periods prior to the intervention serve as visual and statistical checks of the parallel trends assumption, which we expect to hold given the randomized

selection of intervention and control groups. However, to address potential failures of the parallel trends assumption, we will conduct a specification test in which we will estimate and trend out of the post-intervention period any differential pre-intervention trends in outcomes between the two groups.¹⁷ The coefficients on the terms interacting treatment status with time periods after the intervention period will recover the overall (dynamic) intervention effect.

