School performance	Grade point average	Philadelphia School District Data	Continuous	Annual data from 2 years prior to enrollment through 1 year after intervention period complete
Preterm birth	Rate of preterm birth (birth < 37 weeks gestational age)	Pennsylvania birth certificate data	Continuous (rate)	Quarterly data from 8 quarters prior to enrollment and 4 quarters after intervention period complete
Low birth weight	Rate of low birthweight (birthweight < 2000 grams)	Pennsylvania birth certificate data	Continuous (rate)	Quarterly data from 8 quarters prior to enrollment and 4 quarters after intervention period complete
Emergency room utilization	Emergency room visits in the previous 12 months	Children's Hospital of Philadelphia Electronic Health Record	Continuous (rate)	Annual data from 2 years prior to enrollment through 1 year after intervention period complete
Hospitalization	Number of hospitalizations in the previous 12 months	Children's Hospital of Philadelphia Electronic Health Record	Continuous (rate)	Annual data from 2 years prior to enrollment through 1 year after intervention period complete

Qualitative Analysis

We will use an applied thematic analytic approach to qualitative data analysis. Data analysis will coincide with data collection, enabling us to adjust data collection procedures to capture emerging and unexpected phenomena. Starting with the first 3-5 interviews, qualitative data will be coded in cycles by the coding team, led by [name] and performed by the Penn Mixed Methods Research Laboratory. The first cycle of coding will enable generation of a codebook grounded in the data (de novo codes) and in a priori codes reflecting

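### Table 2 defines low birth weight as under 2000 g without giving a reason, although the term ordinarily means under 2500 g, so the outcome is not the measure its name states.

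*Combined protocol and SAP*

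**What the plan says.** Section 9 (Secondary child health outcomes) plans to study "birth outcomes for cluster residents using Pennsylvania birth certificate data". Table 2 carries two such outcomes in adjacent rows, both reported quarterly:

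- Preterm birth: "Rate of preterm birth (birth < 37 weeks gestational age".
- Low birth weight: "Rate of low birthweight (birthweight < 2000 grams".

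The second row contains the only birth-weight cut-off in the documents. It has no reason, no source, and no qualifier marking it as a stricter category. Section 4 (Background) speaks of racialized stressors and healthcare discrimination "resulting in higher rates of preterm birth and low birth weight", and gives no cut-off or rate for either condition.

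For outcomes built from microcluster-level administrative data, Section 9 (Microcluster level secondary outcomes) states: "we will estimate a Poisson-fixed effects model for each secondary outcome". It adds cluster and quarter fixed effects, and standard errors clustered by microcluster.

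**The concern.** Low birth weight is a standard term, and readers will take it to mean under 2500 g. An analyst who follows Table 2 will score a birth of 2000–2499 g as not low birth weight, and the result will still be published under the standard name. Two things are at stake.

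- **Meaning.** The rate could not be set beside rates from other sources that use the usual definition, and nothing in the name would warn the reader.
- **Precision.** In a Poisson model, information comes from events. A lower cut-off leaves fewer of them. With cluster fixed effects, a microcluster with no events in any quarter contributes nothing to the estimate, and a rarer outcome makes such microclusters more likely.

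The neighbouring row makes the choice stand out: preterm birth comes from the same data source and has its customary limit.

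**Working it through.** The plan states no base rate, event count or power for this outcome, so there is no figure of its own to reproduce. The check has two parts.

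**1. The definition.** The cut-off in Table 2 is under 2000 g. The ordinary meaning of the term is under 2500 g (assumption). The births in dispute are those of 2000–2499 g. No other section gives a different cut-off or explains this one.

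**2. The size of the gap.** The documents contain no birth-weight distribution, so every distribution below is an assumption.

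- Share left out: d = 1 − P(weight < 2000) / P(weight < 2500).
- Precision: the variance of a log rate ratio from Poisson counts is a sum of terms 1/E, where E is an event count. If every count falls to a fraction (1 − d), the standard error is multiplied by 1/√(1 − d). This holds for a two-group ratio and for a difference-in-differences contrast, provided d is the same in each cell.

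Worked example, normal with mean 3100 g and SD 600 g:

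- P(< 2500) = 0.1587 and P(< 2000) = 0.0334.
- d = 1 − 0.0334/0.1587 = 1 − 0.21 = 0.79.
- Standard-error multiplier = 1/√0.21 ≈ 2.2.

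Two families were tried:

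- **Single normal:** means 3000, 3100, 3200 and 3300 g; SDs 450 to 650 g in steps of 50 (4 × 5 = 20 scenarios).
- **Mixture with a heavier lower tail:** a main part with mean/SD of 3100/480, 3200/480 or 3300/450 g, plus a low-weight part of 2, 4, 6 or 8% with mean 1500, 1800 or 2200 g and SD 700 g (3 × 4 × 3 = 36 scenarios).

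| Scenario | d | SE multiplier |
|---|---|---|
| Mixture, smallest d (8% at 1500 g; main 3300/450) | 0.422 | 1/√0.578 ≈ 1.3 |
| Mixture, largest d (2% at 2200 g; main 3100/480) | 0.842 | 1/√0.158 ≈ 2.5 |
| Normal, smallest d (3000/650) | 0.719 | 1/√0.281 ≈ 1.9 |
| Normal 3200/550 | 0.857 | 1/√0.143 ≈ 2.6 |
| Normal, largest d (3300/450) | 0.949 | 1/√0.051 ≈ 4.4 |

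The share left out exceeds one half in all 20 normal scenarios and in 34 of the 36 mixtures, so in 54 of 56. The two exceptions are mixtures with d = 0.477 and d = 0.422. The largest multipliers come from narrow normal curves, which put very little weight below 2000 g. The mixtures do not go above about 2.5.

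The multiplier treats the counts as pure Poisson. Variation between microclusters that does not shrink as events accumulate would bring it closer to 1. It compares precision only; the true effect on births under 2000 g could differ from the effect on births under 2500 g.

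**The case against.** The strongest reply is that the documents do not contradict themselves. They never define low birth weight as under 2500 g, and a trial may choose a stricter threshold. The conventional limit in the preterm row is circumstantial and does not prove that 2000 g is a slip. That is right as far as it goes: the documents do not show whether the figure is an error or a choice. It does not remove the fault. A slip needs correcting, and a deliberate choice needs a reason and a name that tells the reader what was counted.

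Four stronger readings are tempting, and the documents do not support them.

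- A reader might infer that the cut-off certainly discards most low-birth-weight births. That needs a distribution the documents do not give, and two of the 56 scenarios go the other way. Probably most is the limit of what can be said.
- A reader might infer that the treatment comparison is biased. The same cut-off applies to both arms and every quarter, so the contrast remains valid for births under 2000 g.
- A reader might say that the rate cannot be compared with the disparity in the Background. That sentence offers no cut-off or rate to compare with; the loss is comparability with conventionally defined rates in general.
- A reader might add that quarterly birth counts per microcluster are already very small. This is plausible for areas built from an eighth-of-a-mile buffer, but no births or expected events are stated.

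The stakes are also modest. This is one of six microcluster-level child outcomes in Table 2, and all of them are secondary.

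**Conclusion.** The point holds for the label and the definition: the outcome is called low birth weight, is set at under 2000 g, and carries no justification. This rests on one outside assumption, the ordinary 2500 g meaning of the term, and not on any distribution.

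The size does depend on assumed distributions. About 42–95% of births under 2500 g would go uncounted. The standard error of the log rate ratio would be roughly 1.3 to 2.6 times as large as with the 2500 g limit, and more at the extreme of the normal scenarios. The harm is to naming, comparability and precision. The between-arm comparison, the two primary outcomes and the power calculation are untouched. It should be corrected, but it does not threaten the trial's main conclusions.

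**What to change.** In Table 2, change the definition of low birth weight to birthweight under 2500 g. If under 2000 g was intended, keep it as a separate row with its own name, for example birthweight under 2000 g, and state why that threshold was chosen. Make and date the change before the birth-certificate data are analysed, so that it cannot be read as a definition chosen after seeing results.

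The cost is one figure in one table row, or one extra row with a sentence of reasoning. The same birth-certificate field supplies both cut-offs, so no new data are needed. An added row would be one more outcome in the planned multiple-comparisons adjustment.

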11.1 Data confidentiality

Paper-based records will be kept in a secure location and only be accessible to personnel involved in the study. Computer-based files will only be made available to personnel involved in the study through the use of access privileges and passwords. Wherever feasible, identifiers will be removed from study-related information. Precautions are in place to ensure the data are secure by using passwords and encryption, because the research involves web-based surveys.

11.2 Subject confidentiality

All participants will provide informed consent for access to the data they generate as part of this research study. All study staff will be reminded to appreciate the confidential nature of the data collected and contained in these databases. The Penn Medicine Academic Computing Services (PMACS) will be the hub for the hardware and database infrastructure that will support the project. The PMACS is a joint effort of the University of Pennsylvania's Abramson Cancer Center, the Cardiovascular Institute, the Department of Pathology, and the Leonard Davis Institute. The PMACS provides a secure computing environment for a large volume of highly sensitive data, including clinical, genetic, socioeconomic, and financial information. Among the IT projects currently managed by PMACS are: (1) the capture and organization of complex, longitudinal clinical data via web and clinical applications portals from cancer patients enrolled in clinical trials; (2) the integration of genetic array databases and clinical data obtained from patients with cardiovascular disease; (3) computational biology and cytometry database management and analyses; (4) economic and health policy research using Medicare claims from over 40 million Medicare beneficiaries. PMACS requires all users of data or applications on PMACS servers to complete a PMACS-hosted cybersecurity awareness course annually, which stresses federal data security policies under data use agreements with the university. The curriculum includes Health Insurance Portability and Accountability Act (HIPAA) training and covers secure data transfer, passwords, computer security habits and knowledge of what constitutes misuse or inappropriate use of the server. We will implement multiple, redundant protective measures to guarantee the privacy and security of the participant data. All investigators and research staff with direct access to the identifiable data will be required to undergo annual responsible conduct of research, cybersecurity, and HIPAA certification in accordance with University of Pennsylvania regulations.

Data will be stored, managed, and analyzed on a secure, encrypted server behind the University of Pennsylvania Health System (UPHS) firewall. This server was created for projects conducted by the Urban Health Lab. All study personnel that will use this data are listed on the IRB application and have completed training in HIPAA standards and the CITI human subjects research. Data access will be password protected. Whenever possible, data will be de-identified for analysis.

11.3 Subject privacy

Participation will be kept confidential. Data are being collected specifically for research purposes and will be managed by the PIs and study team. Subject identifier paperwork includes contact list with name, street address, telephone number, possibly email (depending on participants preferred method of contact), up to 2 contact people, and full consent forms. We will inform participants that we are collecting this information in order to contact participants. No people outside the study team will have access to this information. This information will be linked to a study ID.

Data will be transferred via a firewall-protected, secure, electronic file-transfer to computer server space dedicated to the proposed study. Only MPIs Drs. [name] and [name] will have master access to this server. Co-investigators, project managers, research coordinators, and research assistants will be granted data access at the discretion of the MPIs. Any paper-based records (such as the informed consent and HIPAA authorization form), will be kept in a locked cabinet, inside a locked office, within a Blockley access only building on Penn's campus. All identifying information will be destroyed at the end of the study period.

This research is covered by a Certificate of Confidentiality from the National Institutes of Health. This means that the researchers cannot release or use information, documents, or samples that may identify participants in any action or suit unless they say it is okay. They also cannot provide them as evidence unless participants have agreed. This protection includes federal, state, or local civil, criminal, administrative, legislative, or other proceedings. An example would be a court subpoena.

11.4 Data disclosure

The following entities, besides the members of the research team, may receive protected health information (PHI) for this research study: The Office of Human Research Protections at the University of Pennsylvania - Federal and state agencies (for example, the Department of Health and Human Services, the National Institutes of Health, and/or the Office for Human Research Protections), or other domestic or foreign government bodies if required by law and/or necessary for oversight purposes. Information will also be shared with our study partners providing services for participants:

- Clarifi
- Campaign for Working Families
- Benefits Data Trust
- Pennsylvania Horticultural Society

11.5 Data safety and monitoring

The PIs will be responsible for monitoring data and safety and reporting all serious adverse events, protocol deviations/violations and unanticipated events to the IRB. A written research protocol will go through an IRB review at the University of Pennsylvania to ensure protection of the rights and welfare of human research subjects. The research team, led by the investigators, will be aware of and will monitor possible areas of risk to the research participants. Weekly team meetings will include discussion of any safety and data issues that are observed.

11.6 Risk/benefit

11.6.1 Potential study risks

There are almost no risks to from participation in this study. We will make every effort to keep personal information confidential. Participants may find it uncomfortable to answer some of the questions. They will be able to skip any question they do not feel comfortable answering or end the interview at any time.

A final risk involves the safety of our community coordinator team. Their safety is of the utmost importance so various measures are in place to minimize their risk. The community coordinators will be able to end a home visit at any time if they feel the safety of the subject or themselves is at risk, or if the subject is experiencing psychological distress.

11.6.2 Potential study benefits

Participants may possibly benefit by increasing their financial education, receiving money in their tax return, and accessing a range of benefits they were eligible for but did not previously receive. They may also benefit from an emergency cash grant. Participation could also help us better understand the impact of neighborhood environments and economic inequalities on health outcomes. Participants may get satisfaction knowing they are contributing to our understanding of racial health disparities.

